1.3. Synopsis

	Combining Loncastuximab Tesirine and Epcoritamab in
	Relapsed/Refractory Diffuse Large B-cell Lymphoma
	(DLBCL)
Short title of study:	CLEAR
Sponsor's Study Code:	WWU23 0006
EU CT Number:	2023-509861-19-00
Sponsor:	Universität Münster
Coordinating investigator:	UnivProf. Dr. med. [name]
decidinating investigator.	Citiv. 1 Tol. 21. Mod. [name]
	Medizinische Klinik A
	Hämatologie, Hämostaseologie,
	Onkologie und Pneumologie
	Universitätsklinikum Münster
Indication:	Second-line therapy for patients 18 years or older with CAR-T
mareauern.	cell naive relapsed or refractory aggressive diffuse large B-cell
	. , , , , , , , , , , , , , , , , , , ,
	lymphoma (DLBCL), high-grade B-cell lymphoma (HGBL) or
	follicular lymphoma (FL) grade 3B
	or
	Third-line therapy for patients 18 years or older with relapsed
	or refractory aggressive DLBCL, HGBCL or FL grade 3B who
	failed CAR-T cell therapy in second line
	At least 50% of all study patients will be CAR-T cell naive.
Study design:	Prospective, multicenter, single-arm, open-label, phase II
	study with a safety run-in (irrespective of CAR-T status) and
	efficacy run-in (CAR-T naive patients only) phases.
	chiodoy full in (of the Finance patients only) phases.
Investigational Medicinal	Loncastuximab tesirine intravenously (iv)
Products:	Zeniedetazaniae teenine analy (11)
1 Toddots.	Epcoritamab subcutaneously (sc)
Treatment:	Treatment will be initiated with loncastuximab tesirine iv 7 days
Troutinont.	prior to initiation of epcoritamab.
	phor to initiation of epocitarias.
	Loncastuximab tesirine
	Loncastuximab tesirine 150 µg/kg iv for 2 cycles followed by
	75 µg/kg iv on day 1 of each 21-day cycle in responding
	patients for 6 cycles subsequently (max. 8 cycles).
	Epcoritamab
	Step-up dosing for epcoritamab sc will be performed,
	consisting of a 0.16 mg sc priming dose on day 1 of cycle 1
	(day 8 of cycle 1 for loncastuximab tesirine), followed by a 0.8
	mg sc dose on day 8, and full dosing with 48 mg sc on day 15.
	Starting from day 15, epcoritamab will be administered weekly
	during cycle 2-3, then once every 2 weeks during cycle 4-9,
	and once every 4 weeks from cycle 10 until

Primary objective:	disease progression or relapse, unacceptable toxicity, death, major protocol deviation, pregnancy, patient or investigator decision. For both agents the doses approved according to SmPC are not allowed to be exceeded (i.e. 150 µg for loncastuximab tesirine and 48 mg for epcoritamab). Best overall response rate (complete plus partial remission rate) (BORR) in the study population achieved up to 12-months
	of treatment with loncastuximab tesirine and epcoritamab
Secondary objectives:	Secondary objectives for efficacy:
	- Progression-free survival (PFS)
	- Overall survival (OS)
	- Complete remission (CR) rate
	- Partial remission (PR) rate
	- Time to complete response
	- Time to best response
	- Duration of response (DOR)
	- BORR after 18- and 24-months of treatment
	- Progression rate
	- Relapse rate
	Outcomes according to biological characteristics of the lymphoma
	Secondary objectives for safety and tolerability:
	- Rate of treatment-related deaths
	- Safety and tolerability, and protocol adherence of epcoritamab and loncastuximab tesirine
Primary endpoint:	Best overall response rate (BORR) of relapsed/refractory DLBCL, HGBL and FL grade 3B patients defined as the proportion of patients who achieve a complete or partial remission as best response up to 12-months of treatment according to the 2014 Lugano criteria after failing first-line immunochemotherapy administered at least one time or second-line therapy with CAR-T cells.
Secondary endpoints:	Secondary endpoints for efficacy:
	- PFS
	- OS
	- CR rate
	1

	- PR rate
	- Time to complete response
	·
	- Time to best response
	- DOR
	- BORR after 18- and 24-months of treatment
	- Progression rate
	- Relapse rate
	- Outcomes according to biological characteristics of DLBCL
	Secondary endpoints for safety and tolerability:
	- Adverse events (AEs)
	- Serious AEs (SAEs)
	- Rate of treatment related deaths
	Secondary endpoints for protocol adherence:
	- Number of treatment cycles received
	- Duration of treatment cycles
	- Cumulative doses of loncastuximab tesirine and epcoritamab
Study population:	Patients older than 18 years with DLBCL, HGBL or FL grade 3B who failed first-line immunochemotherapy administered at least one time.
	Patients older than 18 years with DLBCL, HGBL or FL grade 3B who failed second-line therapy with CAR-T cells.
Patient number:	120 patients with histologically confirmed relapsed/refractory DLBCL, HGBL or FL grade 3B, including 20 patients treated in the safety run-in phase (irrespective of CAR-T status) and 20 patients treated in the efficacy run-in phase (CAR-T naive only). The number of patients with previous CAR-T treatment will
	be capped at n=60.
Number of Study Centers:	A maximum of 35 institutions will be included with sites active in the German Lymphoma Alliance (GLA) (31 institutions) and the Italian Study Group Fondazione Italiana Linfomi (FIL) (4 institutions)

Inclusion Criteria:

Disease/Condition Activity:

- Subjects with histologically confirmed relapsed/refractory (r/r) disease based on pathology report (WHO 2022 criteria) at the time before study entry. Specifically, patients with
 - a. DLBCL (de novo or transformed)
 - b. HGBL with MYC and BCL2 rearrangements
 - c. HGBL, not otherwise specified (NOS)
 - d. Follicular lymphoma grade 3B will be included

Paraffin-embedded tissue must be available and sent to a reference pathologist in order to allow for pathological diagnosis and the translational research program. CD20 expression (or a high likelihood of CD20 expression) based on immunohistochemistry should be documented prior enrollment into the study.

Refractory disease is defined as no remission to the last therapy. Subjects intolerant to previous therapy are excluded. Two groups of patients are eligible:

- Progressive disease (PD) or stable disease (SD) as best response to previous therapy.
- Complete (CR) or partial response (PR) as the best response after previous therapy, with biopsy-proven relapse occurring < 6 months after end of treatment.

Relapsed disease is defined as subjects achieving complete or partial remission to previous therapy, followed by biopsy-proven relapse ≥6 months after treatment completion.

Subjects with refractory and early relapsed (≤12 first months) disease after line anti-CD20-/anthracycline-containing therapy are eligible. Subjects with late relapsed (>12 months) disease after first line anti-CD20-/anthracycline-containing therapy can be enrolled in the study only if deemed ineligible to high dose chemotherapy (HDCT) followed by autologous stem cell transplantation (ASCT). Subjects relapsed/refractory to second line CAR-T cell therapy are eligible.

- 2. Subjects must be age 18 years or older.
- 3. Subjects must be eligible to receive and in need of treatment initiation based on symptoms and/or disease burden, as assessed by the investigator.

- 4. Eastern Cooperative Oncology Group Performance status (ECOG) 0-2.
- 5. Subjects must have one or more measurable disease sites, defined as follows:
 - A positron emission tomography/computed tomography (PET/CT) scan demonstrating PETpositive lesion(s).
 - At least one measurable nodal lesion (long > 1.5 cm and short axis > 1.0 cm) or one measurable extra-nodal lesion (long axis > 1.0 cm) on CT scan or MRI.
- 6. Ability to understand and willingness to sign written informed consent. Signed informed consent must be obtained before any study-specific procedure.

Contraception:

- 7. Women of childbearing potential and sexually active men must practice a highly effective method of birth control during and after the study, consistent with local regulations regarding the use of birth control methods for subjects participating in clinical trials. Men with female partners who are of childbearing potential must agree to use a condom when sexually active or practice total abstinence from the time of giving informed consent until at least 7 months after the patient receives his last dose of study treatment. Men must agree not to donate sperm from the time of giving informed consent until at least 7 months after the patient receives his last dose of study treatment. For female subjects, they apply for 12 months after the last dose of the study drug.
- 8. Women of childbearing potential must have a negative serum or urine beta-human chorionic gonadotropin (beta-hCG) pregnancy test at screening.

Adequate baseline organ function tests should be collected no more than 7 days before starting study treatment. The following criteria should be met:

- Total bilirubin ≤ 1.5 times the upper limit of normal (ULN) (< 3 times ULN for patients with Gilbert syndrome, cholestasis due to compressive adenopathies of the hepatic hilum, documented liver involvement, or biliary obstruction due to lymphoma).
- 10. Alanine aminotransferase (ALT) and aspartate aminotransferase (AST) and gamma glutamyl

- transferase (GGT) \leq 2.5 times ULN (\leq 5 times ULN for patients with liver involvement by lymphoma).
- 11. Glomerular filtration rate (GFR) ≥ 45 mL/min/1.73 m² according to the Chronic Kidney Disease Epidemiology Collaboration (CKD-EPI) formula. If not within the target range, this evaluation may be repeated once after at least 24 hours, either using the CKD-EPI formula or through 24-hour sampling. If the subsequent result falls within an acceptable range, it may be used to fulfill the inclusion criteria.
- 12. Prothrombin time/International normalized ratio (INR)/Activated partial thromboplastin time (aPTT) ≤ 1.5 times ULN, unless the patient is receiving anticoagulation (although INR should not exceed 4.0).
- 13. Platelet count ≥ 75,000/mm³ without transfusion in the prior 7 days.
- 14. Hemoglobin ≥ 8 g/dL.
- 15. Absolute neutrophil count ≥ 1,000/mm³ (off growth factors at least 72 hours).
- 16. Left ventricular ejection fraction > 45%.

Concomitant Medications:

17. Subjects should not take medication known to decrease T-cell numbers or activity, or other concurrent immunosuppressive medication, except for up to 10 mg prednisone daily or its equivalent, unless it is for disease control during screening,

- premedication and/or CRS/ICANS management within the study.
- 18. Subjects must not have been treated with any investigational drug within 30 days or 5 half-lives of the drug (whichever is longer) prior to the first dose of study drugs, nor be currently enrolled in another interventional clinical study or have been previously enrolled in this study (agents that have been approved under emergency authorization, e.g., anti-SARS-CoV-2 monoclonal antibodies, are allowed).
- 19. Acute toxicity (except alopecia, fatigue) of any prior lymphoma therapy should be resolved to Grade ≤ 1 (with the exception of prior CRS or ICANS that should be fully resolved) at study screening.
- 20. Subjects should not have received vaccination with live-attenuated vaccines within 28 days prior to screening, nor are expected to need any liveattenuated vaccination during study participation, including at least 3 months following the last dose of study treatment. However, coronavirus mRNA and adenovirus-based vaccines, which are not liveattenuated vaccines, are permitted.

Exclusion Criteria:

Patients who meet any of the following criteria at the time of screening will be excluded:

- Any prior lymphoma-directed treatment, except for first-line anti-CD20-/anthracycline-containing therapy or second line CAR-T cell therapy. Particularly, patients previously treated with loncastuximab tesirine and any CD3xCD20 bispecific antibody therapy are not eligible.
- 2. Patients with late relapse (>12 months) after first-line immunochemotherapy considered HDCT/ASCT eligible as assessed by the local investigator.
- 3. Known central nervous system (CNS) involvement.
- 4. Diagnosed or treated for any malignancy other than DLBCL, transformed indolent lymphoma, HGBL or FL grade 3B within the last 3 years, except for the following:
- Adequately treated non-melanoma skin cancer or lentigo maligna without evidence of disease.
- Non-invasive basal cell or squamous cell skin carcinoma.
- Adequately treated carcinoma *in situ* without evidence of disease.
- Localized prostate cancer, post-radical prostatectomy with non-rising prostate-specific antigen levels < 0.1 ng/mL.
- Cervical carcinoma of stage 1B or less.
- Non-invasive, superficial bladder cancer.
- Any curable cancer with a CR of > 2 years duration.
- 5. Known history of human immunodeficiency virus (HIV) or active hepatitis C virus (HCV) or active hepatitis B virus (HBV) infection or any known active systemic bacterial, viral, fungal, mycobacterial, parasitic, or other infection (excluding fungal infections of nail beds). Patients with serologic markers of HBV immunization due to vaccination (HBsAg negative, Anti-HBc negative, and Anti-HBs positive) will be eligible. Subjects who are positive for hepatitis B core antibody, hepatitis B surface antigen, or hepatitis C antibody must have a negative polymerase chain reaction (PCR) result before enrollment. Those who are PCR positive will be excluded.
- 6. CMV-PCR positive at baseline.
- 7. Any life-threatening illness, medical condition, or organ system dysfunction that, in the investigator's opinion, could compromise the subject's safety or interfere with the feasibility to administer study drugs, including active hemophagocytic lymphohistiocytosis/macrophage activation syndrome (HLH/MAS).

- 8. Concurrent treatment with another investigational agent or radiation therapy.
- 9. Any psychological, cognitive, familial, or social condition that, in the investigator's opinion, compromises the patient's ability to understand the patient information, give informed consent, or comply with the study protocol.
- 10. Participation in another clinical trial.
- 11. Known history of hypersensitivity and/or positive serum human anti-drug antibody (ADA) against any component of the study products or concomintant medication or an anti-CD19 antibody.
- 12. History of Stevens-Johnson syndrome or toxic epidermal necrolysis.
- 13. Clinically significant third space fluid accumulation (i.e., ascites requiring drainage or pleural effusion that is either requiring drainage or associated with shortness of breath).
- 14. Pregnancy or breastfeeding.
- 15. Use of any other experimental medication within 30 days or 5 half-lives prior to the start of study drug (Cycle 1 Day 1).
- 16. Close affiliation with the investigational site, such as a close relative of the investigator or dependent persons (e.g., employee or student of the investigational site).

Excluded medical conditions:

- 17. Congestive heart failure > New York Heart Association (NYHA) class 2.
- 18. Unstable angina (angina symptoms at rest), new-onset angina (begun within the last 3 months).
- 19. Uncontrolled atrial or ventricular cardiac arrhythmia.
- 20. Left ventricular ejection fraction ≤ 45%.
- 21. Electrocardiographic evidence of acute ischemia, coronary angioplasty, or myocardial infarction within 6 months prior to screening.
- 22. Arterial or venous thrombotic or embolic events such as cerebrovascular accident (including transient ischemic attacks), deep vein thrombosis, or pulmonary embolism within 3 months before the start of study medication.
- 23. Congenital long QT syndrome or a QTcF interval of > 480 ms at screening (unless secondary to pacemaker or bundle branch block).
- 24. Severe chronic pulmonary disease.
- 25. Known clinically significant liver disease, including hepatitis, current alcohol abuse, or cirrhosis.

- 26. Autoimmune disease requiring immunosuppressive therapy except for up to 10 mg prednisone daily (or equivalent).
- 27. Seizure disorder requiring therapy within the past 12 months. Subjects with history of seizure disorder beyond that must have complete CNS workup.
- 28. Major surgery within 4 weeks of the first dose of study drugs excepting lymphoma-related reasons.
- 29. Any other co-existing medical or psychological condition that will preclude participation in the study or compromise ability to give informed consent.

Visits:

Screening visit:

Patients will undergo a screening visit prior to any treatment to verify study eligibility.

Treatment period:

Patients will receive loncastuximab tesirine for up to 8 cycles if no disease progression or relapse, unacceptable safety and tolerability, death, major protocol deviation, or patient, investigator, or sponsor decision in the meantime. Epcoritamab will be administered until disease progression or relapse, unacceptable safety and tolerability, death, major protocol deviation, or patient, investigator, or sponsor decision.

Restaging:

There will be repeated staging (response assessment) every 6 weeks for first 6 months after starting treatment, then every 3 months for subsequent 6 months, and every 6 months thereafter and as clinically indicated until the end of treatment. Staging should be preferably PET-based; contrast-enhanced CT is also accepted if PET-CT or PET-MRI is not available.

Follow-up visits:

For all study patients, a first follow-up should be performed 6 weeks after the end of therapy with loncastuximab tesirine and epcoritamab. Three-monthly follow-up examinations are recommended during the first 2 years after the end of therapy, and six-monthly evaluation in the following 3 years.

Safety evaluations include adverse event (AE) monitoring, physical examination, evaluation of changes to concomitant medications, and clinical laboratory parameters (hematology, coagulation, and serum chemistry). AEs that occur between the signing of the informed consent through 150 days after the last application of loncastuximab tesirine and/or epcoritamab will be collected. The severity of adverse events will be assessed using the National Cancer Institute Common Terminology Criteria for Adverse Events, Version 5.0. Serious adverse events will be reported according to the Good Clinical Practice (GCP) regulations.

Analysis of feasibility and safety:

Safety run-in phase for all patients:

A first safety analysis will be conducted 60 days after 20 patients started treatment with loncastuximab tesirine and epcoritamab. A detailed analysis of all (serious) adverse events, particularly the occurrence of cytokine release activation syndrome (CRS), macrophage syndrome (MAS)/hemophagocytic lymphohistiocytosis (HLH), immune effector cell-associated neurotoxicity syndrome (ICANS), tumor lysis syndrome (TLS), as well as liver- and phototoxicity, edema, effusion and infections, will be performed. The toxicities observed will be compared to the (S)AEs experienced in the loncastuximab tesirine phase 2 trial (Caimi et al. Lancet Oncol 2021; 22:790) and the epcoritamab phase 1/2 study (Hutchings et al. Lancet 2021; 398:1157). These data will be submitted to the Clinical Trial Information System (CTIS) as part of a substantial modification for review and decision-making on the continuation of the study. The Data Safety Monitoring Committee (DSMC) will evaluate the safety profile of the combination of epcoritamab and loncastuximab tesirine and decide on the continuation of the study.

Efficacy run-in phase for CAR-T naive patients:

For patients not pretreated with CAR-T cells, an additional and separate efficacy analysis will be performed after the 20th CAR-T naive patient started treatment with loncastuximab tesirine and epcoritamab and had a second response assessment (12 weeks after treatment initiation) by FDG-PET/CT (-/MRI). The primary endpoint of the CLEAR study is BORR. Studies with CAR-T cells performed in second line patients with early relapse/refractory disease, the ZUMA-7 (n=180) and TRANSFORM (n=92) trials, demonstrated an ORR of 83% and 87% respectively. Thus, the pooled ORR of a CAR-T cell therapy is estimated at 84% (95% CI: 79-88%). For the efficacy run-in phase of the CLEAR study a BORR < 60% is considered not acceptable. If ≤ 11/20 patients achieve a CR or PR the BORR will be $\leq 55\%$ (95% CI: 32-77%), no longer including the lower limit of the 95% CI for BORR observed in ZUMA-7 and TRANSFORM trial (pooled data) and the study will be closed for CAR-T naive patients. In any case, the BORR will be reported to the DSMC, the members of which will meet to evaluate the efficacy of CLEAR study in the first 20 CAR-T naive patients included. The DSMC shall recommend continuation of the study, require modifications, or stop the study after independent review of all available data. The results of the efficacy run-in phase evaluated by the DSMC will be communicated and discussed with the principal investigator, the study committee, and the sponsor of the study. The final recommendation to continue, modify or stop the study lies with the DSMC. The data will also be submitted to CTIS. The study sponsor will follow the DSMC's suggestion to continue, modify or stop the study for CAR-naive patients.

	Intoning a fate, and affice as a making in all matients.
	Interim safety and efficacy analysis in all patients: An interim analysis will be conducted 6 months after the 50th patient has been recruited. Patients participating in the safety run-in phase will be considered for interim analysis as well. If the ORR is 60% or below, the study will be terminated early.
	The relevant data will be submitted to the CTIS as part of a substantial modification for review and decision-making on the continuation of the study. At interim analysis, the members of the DSMC will evaluate the efficacy and safety profile of the combination of epcoritamab and loncastuximab tesirine and the protocol adherence and decide on the continuation of the
Statistical Methods:	The ORR, CR rate, PR rate, progression rate, rate of treatment-related deaths and relapse rate will be documented together with the corresponding 95% confidence intervals (Clopper-Pearson). Data on time to event endpoints (PFS, OS, duration of complete response, duration of response) will be analyzed using Kaplan-Meier curves/cumulative incidence curves. Median time for these endpoints will be presented with 95% confidence intervals. For qualitative endpoints (adverse events, serious adverse events) frequency tables will be prepared. Quantitative endpoints (laboratory parameters, cumulative doses of drugs, duration of therapy, time to complete response, time to best response) will be described in tables displaying sample size, range, mean and standard deviation or medians and quartiles.
Analysis population	All analyses will use the intent-to-treat population, which will include all patients who receive any treatment.
Timelines:	First patient in: Q3/2025 Last patient in: Q1/2027 Planned overall duration of the study: 4.5 years
Financial support:	AbbVie Sobi

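### The synopsis gives conflicting loncastuximab rules for stable disease after cycle 2, and states the dose ceiling in a unit that the scheduled doses cannot meet

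*Protocol*

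**What the plan says.** All the statements are in the protocol synopsis (section 1.3).

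- **Treatment, first two cycles:** "Loncastuximab tesirine 150 µg/kg iv for 2 cycles followed by" a lower dose.
- **Treatment, later cycles:** "75 µg/kg iv on day 1 of each 21-day cycle in responding" and then "patients for 6 cycles subsequently (max. 8 cycles". Cycles 3 to 8 are therefore conditional on response.
- **Treatment period (under Visits):** "Patients will receive loncastuximab tesirine for up to 8 cycles if no disease progression or relapse, unacceptable safety and tolerability", followed by death, major protocol deviation, and patient, investigator or sponsor decision. Response is not a condition and its absence is not a reason to stop.
- **Restaging:** "every 6 weeks for first 6 months after starting treatment", then at longer intervals.
- **Dose limit (the sentence after the epcoritamab schedule):** "For both agents the doses approved according to SmPC are not allowed to be exceeded", with the limits given as "i.e. 150 µg for loncastuximab tesirine and 48 mg for epcoritamab". The loncastuximab limit has no per-kilogram unit.

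**The concern.** A patient with stable disease has neither responded nor progressed. Under the Treatment entry this patient has no loncastuximab scheduled after cycle 2. Under the Treatment period entry the patient continues. Nothing in the synopsis says which text governs.

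This matters for three reasons:

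- The primary endpoint is the best response up to 12 months of treatment. A patient with stable disease at an early scan who later reaches partial or complete remission counts as a responder, so the unclear rule applies to patients who can still change the endpoint.
- The efficacy run-in for CAR-T naive patients is read at week 12, after the two rules have diverged, and closes that group at 11 or fewer responders of 20.
- The number of cycles and the cumulative doses are secondary endpoints for protocol adherence. For a stable-disease patient both depend on the reading, and so does whether continuing or stopping departs from the protocol.

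The ceiling is a separate matter. It is worded as an absolute prohibition, and the schedule as written cannot comply with it.

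**Working it through.** **Inputs from the synopsis:** 2 cycles at 150 µg/kg; 6 further cycles at 75 µg/kg; maximum 8 cycles; 21-day cycles; restaging every 6 weeks at first; run-in read at week 12; run-in closure at 11 or fewer of 20; interim termination at an ORR of 60% or below; 120 patients; ceiling 150 µg.

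**Assumed, because the documents do not give them:** stable disease at week 6 in 5-20% of patients; a difference of 10-40 percentage points in later conversion to CR or PR between stopping and continuing loncastuximab; body weight 50-100 kg.

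**1. The plan's own figure.** 2 + 6 = 8 cycles, which reproduces the stated maximum. The two entries agree on this maximum.

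**2. Where the rules part.** 2 × 21 = 42 days = 6 weeks, so the first restaging falls just before cycle 3 (day 43).

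| Status after cycle 2 | Treatment entry | Treatment period entry |
|---|---|---|
| CR or PR | continue, to 8 cycles | continue, to 8 cycles |
| Progression | stop | stop |
| Stable disease | no further cycles scheduled | continue, to 8 cycles |

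Only the last row conflicts.

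**3. Exposure in stable disease.**
- At most 2 cycles: 2 × 150 = 300 µg/kg.
- Up to 8 cycles: 2 × 150 + 6 × 75 = 750 µg/kg. This takes 75 µg/kg from cycle 3, although the Treatment entry states that dose only for responders. It is an upper limit, because a patient who later progresses stops sooner.

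**4. Patients touched.**
- Whole trial: 120 × 5% = 6, up to 120 × 20% = 24.
- Run-in: 20 × 5% = 1, up to 20 × 20% = 4.

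**5. Illustrative effect on BORR.** Difference = share with stable disease × difference in conversion.
- Low end: 5% × 10 points = 0.5 points.
- High end: 20% × 40 points = 8 points.

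This compares one reading followed everywhere with the other followed everywhere. A mixture of readings would fall between.

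**6. Run-in timing.** Week 12 is day 84, and 4 × 21 = 84, so the second assessment comes at the end of cycle 4, with cycles 3 and 4 already subject to the conflict. One patient is 1/20 = 5 points, the whole distance between 11/20 = 55% (close) and 12/20 = 60% (continue).

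**7. Ceiling.** Dose = µg/kg × body weight.
- 150 µg/kg at 50-100 kg: 7,500-15,000 µg, which is 50-100 times 150 µg.
- 75 µg/kg at 50-100 kg: 3,750-7,500 µg, which is 25-50 times 150 µg.
- The first exceeds 150 µg at any weight above 1 kg and the second at any weight above 2 kg, so the conclusion does not depend on the assumed weights.

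**The case against.** The best defence is that the two continuation texts can be read together: the Treatment entry is the specific dosing rule, and the Treatment period entry only states a maximum and reasons to stop. Investigator decision is among those reasons, so a non-responder could be stopped under either text. This softens the conflict but does not remove it. The Treatment period entry sets out its own conditions and leaves non-response out, and investigator decision is a discretionary exit, not a rule. A patient with stable disease who continues under that entry also has no stated dose.

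On the ceiling, the matching numeral suggests that a unit was dropped, and fault in the PDF extraction cannot be wholly excluded. But the sentence reads cleanly, and the per-kilogram unit survives twice in the Treatment entry.

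Several cautions stand. No text ties response to the week-6 scan; that link is inferred from the timing. It cannot be known that sites will differ in their reading. The text shown does not define a major protocol deviation, so it cannot be said that a departure here would count as one.

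A reader might infer that the trial has no single regimen behind its primary endpoint. The documents do not support that: cycles 1-2, the epcoritamab schedule, the handling of responders and of patients who progress, and the 8-cycle maximum are the same under both texts. A reader might also take the share of patients with stable disease as the possible shift in BORR. It is only the share touched. BORR moves through the difference in conversion among them, and epcoritamab continues under both readings.

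**Conclusion.** Both contradictions stand as internal inconsistencies in the current synopsis text.

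The continuation conflict is confined to patients with stable disease, from cycle 3, for one of the two drugs. Within that group it is large: at most 2 cycles against up to 8, or 300 against up to 750 µg/kg cumulative. Its effect on BORR can only be illustrated, at about 0.5-8 points, and that range rests wholly on the assumed stable-disease share and conversion difference. The cycle-count and cumulative-dose endpoints depend on the reading directly. The run-in decision could turn on a single affected patient, but nothing shows that it will.

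The ceiling is a unit conflict in a safety limit that no adult can meet as scheduled. It does not define a second regimen, and the 50-100-fold figure measures how unworkable the literal text is, not a dose anyone is likely to plan.

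No sample size, stopping boundary or endpoint definition is affected.

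**What to change.** - Reconcile the Treatment and Treatment period entries so that one rule, in the same words in both places, says what a patient with stable disease receives after cycle 2. If patients with stable disease continue, the dose must be stated for them too.
- Tie the term for response to a named assessment, so that every site applies it at the same time point.
- Reconcile the unit of the loncastuximab ceiling with the unit of the scheduled doses.
- Carry the reconciled wording through wherever the protocol repeats these rules.

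Which continuation rule and which unit are intended is for the sponsor to decide. The cost is protocol wording only, best settled before the first patient is treated. If treatment has begun, also record for each patient with stable disease which rule was followed, so that cycle counts, cumulative dose and late responses can be interpreted.
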